### **6.2.4 Duration/Study Day/Time**

Study day will be calculated as the number of days from first dose of study drug (Day 1).

- Date of event – date of first dose of study drug + 1, for events on or after first dose
- Date of event – date of first dose of study drug, for events before first dose
- To this end, Day 0 remains undefined.

For all time to event analyses, subjects not reporting the specified endpoint will be censored at the time that the subjects were last known not to have experienced the endpoint. For all endpoints not encompassing death, all deaths will be treated as censoring events. In complex cases where the censoring time of the subject is uncertain, the case will be reviewed by the [REDACTED] statistician and a censoring time will be assigned and programmed prior to database lock.

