### **6.11.4 Other Secondary Endpoints**

The other Secondary endpoint analyses will be performed on the ITT population.

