#### 6.11.4.1 Duration of UPCR $\leq 0.5$ mg/mg

Duration of UPCR  $\leq 0.5$  mg/mg refers to the time (weeks) from the onset of the first UPCR  $\leq 0.5$  mg/mg to the subsequent, second occurrence of UPCR  $>0.5$  mg/mg (i.e., allowing a single spike in UPCR). An event occurs at the time of the subsequent, second UPCR  $>0.5$  mg/mg. Subjects who do not experience a subsequent, second UPCR  $>0.5$  mg/mg will be censored at the date of the last UPCR assessment. Only subjects who achieved an initial response (UPCR  $\leq 0.5$  mg/mg) will be included in the analysis of this endpoint. Duration of UPCR  $\leq 0.5$  mg/mg will be analyzed in a similar manner to that described in Section 6.11.3.1 (Table 14.2.6).

An additional summary of this endpoint will be undertaken by summing the weeks between each UPCR measure  $\leq 0.5$  mg/mg and a subsequent measure  $>0.5$  mg/mg. This will give an approximation of time spent with UPCR  $\leq 0.5$  mg/mg for each subject. This will be summarized and analyzed as a continuous endpoint and comparison between both treatment arms will be carried out using a 2 sample Wilcoxon test.

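### Read literally, the additional time-in-response summary in SAP 6.11.4.1 gives no time to a UPCR ≤0.5 mg/mg still held at the last assessment, and can distort the Wilcoxon comparison in either direction

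*SAP*

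**What the plan says.** SAP 6.11.4.1 describes two analyses of duration of UPCR ≤0.5 mg/mg.

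- **Main analysis.** Time runs from the first UPCR ≤0.5 to the second later value >0.5, analysed by Kaplan-Meier and Cox methods. Subjects without that event "will be censored at the date of the last UPCR assessment". The population is restricted: "Only subjects who achieved an initial response" enter.
- **Additional summary.** The rule opens with "An additional summary of this endpoint will be undertaken by summing the weeks between each UPCR measure"; each interval starts at a value ≤0.5 and stops at a later value >0.5. The purpose is stated next: "This will give an approximation of time spent with UPCR" at or below the threshold, subject by subject. The result is treated as a continuous variable. For the test, the SAP says that "comparison between both treatment arms will be carried out using a 2 sample Wilcoxon test".

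Three other places bear on it. SAP 6.2.4 gives a general censoring rule, limited to one type of analysis: "For all time to event analyses, subjects not reporting the specified endpoint will be censored". SAP 6.2.11 says which observations are used for continuous periods of remission, but not where an open period ends. SAP 6.11.4 sets the general population: "The other Secondary endpoint analyses will be performed on the ITT population". The protocol does not describe the additional summary.

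**The concern.** The rule for the additional summary closes an interval only when a UPCR >0.5 follows. A response still held at the last UPCR has no such value, so the rule assigns it no weeks. Neither censoring rule reaches this case: one belongs to the main duration analysis, the other to time-to-event analyses, and this summary is a continuous variable compared by a rank test without censoring.

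The time dropped is that of the responses still held at the end. Among subjects with an early response, keeping it can lower the rank and losing it can raise it. What is at stake is one reported p-value for time in response, which could disagree with the SAP's own duration analysis because of how the variable is built.

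**Working it through.** The documents give no figure for this summary, so there is none to reproduce. The check has two parts.

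**1. Worked profiles.** The visits are those in SAP 1: Weeks 2, 4, 8, 12, 16, 20, 24, 30, 36, 42, 48 and 52. The profiles are hypothetical.

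Literal score = sum of (week of next value >0.5 − week in which the run at ≤0.5 began), over closed runs only. Closed score = literal score + (52 − start week) for a run still open at Week 52.

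| UPCR ≤0.5 at | Literal | Open run closed at last UPCR |
|---|---|---|
| Weeks 8–52 | 0 | 52 − 8 = 44 |
| Weeks 24–52 | 0 | 52 − 24 = 28 |
| Weeks 8–20, >0.5 at Week 24, ≤0.5 at Weeks 30–52 | 24 − 8 = 16 | 16 + (52 − 30) = 38 |
| Weeks 8–42, lost at Week 48 | 48 − 8 = 40 | 40 |
| Week 8 only, lost at Week 12 | 12 − 8 = 4 | 4 |
| Never | 0 | 0 |

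An open interval adds 0 weeks under every reading tried: runs, each measure counted separately, or adjacent visit pairs only. Counting each measure separately also overlaps. Values ≤0.5 at Weeks 8, 12 and 16 with >0.5 at Week 20 give 12 + 8 + 4 = 24 weeks for a 12-week span.

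**2. Effect on the Wilcoxon test.** This needs rates that the documents do not give, so it illustrates direction only. A two-state model (≤0.5 or >0.5) was run on the same visits. Gain rates were solved so that 34.4% on voclosporin and 20% on placebo are at ≤0.5 at Week 52. Those are the planning rates in SAP 4 for the stricter composite primary endpoint, used as a proxy. Loss rates per 4 weeks are assumptions, and no withdrawal was modelled. Trials had 162 per arm and a two-sided 5% test with tie correction. Subjects with no closed interval score 0 under the literal rule.

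Entries are the share of trials significant for voclosporin, open intervals closed → literal rule; significance for placebo under the literal rule is added where it is material.

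| Assumed loss, voclosporin/placebo | All ITT subjects | Initial responders only |
|---|---|---|
| 5%/5% | 92% → 38% | 7% → 3% |
| 10%/10% | 98% → 74% | 9% → 5% |
| 5%/10% | 66% → under 1%; placebo 10% | 31% → 0%; placebo 43–47% |
| 3%/10% | 38% → 0%; placebo 62% | 42% → 0%; placebo 88% |
| 10%/5% | about 99.8% → 99.6% | 2% → about 60% |

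With lower loss on voclosporin, the literal rule can favour placebo. With higher loss on voclosporin, it favours voclosporin among initial responders and changes almost nothing on ITT. Counting overlapping intervals moved the rejection rates by no more than 1 point in the first four rows. If subjects without a closed interval are set to missing instead of 0, those four rows give 3–7% for voclosporin and 1–2% for placebo, so there is no reversal under that reading.

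**The case against.** The strongest reply is that the SAP's own statement of purpose rules out the literal reading. Time spent at ≤0.5 cannot be 0 for someone at ≤0.5 from Week 8 to Week 52. The paragraph before already ends open responses at the last UPCR, so a sensible programmer would do the same here. The intent is indeed plain. But the stated rule, followed exactly, yields a result that the next sentence contradicts, and the end date would still have to be chosen by whoever programs it.

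The reply is right on four further points, each of which limits the concern.

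- A reader might infer that the rule always costs power or always works against voclosporin. The 10%/5% row shows otherwise, and the documents give no loss rates from which to choose among the rows.
- A reader might infer from the percentages that a reversal is likely in this trial. They rest on assumed loss rates and a proxy response rate, and the reversal disappears if unclosed subjects are set to missing.
- The overlap wording has almost no effect on the test. It matters for the reported number of weeks.
- The population is largely settled. The additional summary is introduced as one of the same endpoint, which the main analysis limits to initial responders. The general ITT statement in SAP 6.11.4 leaves only a point to confirm.

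**Conclusion.** The concern holds for the rule as written, and it is minor. The 0-week score for a sustained response follows from the wording and the visit schedule alone. The effect on the Wilcoxon test can go in either direction, and its size depends on assumed loss rates, on the population analysed and on how subjects without a closed interval are scored.

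A reader might also infer that the trial's efficacy conclusions are exposed. The documents do not support that. Duration of UPCR ≤0.5 is an other secondary endpoint (SAP 3.2.2), it is outside the Hochberg procedure (SAP 6.11.5.2 and 9), and this is only an additional summary of it. The main duration analysis handles open responses by censoring. The primary analysis, the key secondary analyses and the sample size are untouched.

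**What to change.** Reword the additional summary in SAP 6.11.4.1 to do the following:

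1. Sum non-overlapping intervals, each starting at the first UPCR ≤0.5 of a run and ending at the next UPCR >0.5.
2. End an interval still open at the subject's last UPCR assessment, the date at which the main duration analysis censors, and credit no time after it.
3. State whether Week 56 values are used. Subjects who enter the continuation study after completing treatment do not attend that visit (Protocol 4.1 and 9.2.4), which is a reason to stop at Week 52. The main duration analysis has no such cap, so if Week 56 is excluded, say so and note that the two horizons differ.
4. Confirm that the Wilcoxon test covers initial responders, as in the main duration analysis, or state otherwise. The choice changes what is tested: at 5%/5% assumed loss with intervals closed, 92% of simulated trials were significant on ITT and 7% among initial responders. A responder-only comparison should be labelled non-randomised.

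The cost is a few sentences and one derivation. No new data are needed and the Wilcoxon test stays. A footnote should say that subjects who withdraw early can accrue less time.

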## 6.11.2 Primary Efficacy Analysis

### 6.11.2.1 Renal response at Week 52

Renal response at Week 52 will be adjudicated by the Clinical Endpoints Committee (CEC) and as such the analysis will incorporate the CEC's assessments of each subject. In order to perform their adjudication, the CEC will be provided UPCR data, eGFR data, steroid taper data, rescue and prohibited medication data and adverse event data. Full details of the adjudication process are detailed in a separate CEC Charter.

The primary efficacy analysis will be conducted on the ITT population using a logistic regression model with terms for treatment, baseline UPCR, biopsy class, MMF use at baseline and region, and renal response (Yes/No) at week 52 as the response variable (Table 14.2.1.1.2).

The results will be expressed as an odds ratio (and associated two sided- 95% CI) for voclosporin compared to placebo. Odds ratios greater than unity will mean the odds of response are greater for voclosporin than for placebo and therefore indicate a benefit of the voclosporin treatment arm. The p-value of the treatment effect will also be reported.

The following SAS program will be used for the primary efficacy analysis:

```
Proc Logistic data = data;  
Class Treatment_arm MMF_Use Biopsy_Class Region;  
Model Response = Treatment_arm MMF_Use Biopsy_Class Baseline_UPCR Region;  
Run;
```

The number of responders and non-responders at Week 52 will be summarized by treatment arm and a listing of renal responders and non-responders will also be provided.

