#### 6.11.3.1 Time (weeks) to UPCR of $\leq 0.5$ mg/mg

Time to UPCR of  $\leq 0.5$  mg/mg will be analyzed by comparing the survivor function between treatment arms. It will be estimated using Kaplan-Meier methodology and will be presented as a plot showing a line for each treatment group as well as the numbers remaining at risk for each treatment group at different time points. Median time to UPCR of  $\leq 0.5$  mg/mg along with two-sided confidence intervals will be displayed. Time to event will be measured as the number of weeks from day of randomization to the day of the event. Subjects who do not experience an event will be censored on the day of their last assessment of UPCR.

A Cox's proportional hazards model will be fitted to assess the significance of the differences between treatment arms. The model will include terms for treatment arm, baseline UPCR, biopsy class, MMF use at baseline and region. Estimates of the treatment effects will be expressed as hazard ratios (and associated 95% CI) for voclosporin relative to placebo. Hazard ratios greater than unity will indicate the hazard to be greater for voclosporin than for placebo and therefore indicate that the events in question generally occur earlier on active voclosporin and, for this endpoint, a benefit of voclosporin (Table 14.2.2). The log-log survivor function to proportional hazards will be assessed. A listing of time (weeks) to UPCR of  $\leq 0.5$  mg/mg responders and censors will be provided.

#### 6.11.3.2 Partial renal response as defined by 50% reduction from baseline UPCR at Weeks 24 and 52

Change from baseline in UPCR will be calculated as the post baseline measurement minus the baseline measurement. Percent change from baseline will be calculated as:

- Percent change from baseline (UPCRpc) =  $\left( \frac{\text{Change from baseline}}{\text{Baseline}} \right) \times 100$

A 50% reduction in UPCR will be indicated by UPCRpc  $\leq -50$ . Subjects with missing UPCRpc values will be considered non-responders. This endpoint will be analyzed and presented similarly to the primary efficacy endpoint as described in Section 6.11.2 (Table 14.2.3). A listing of subjects considered responders will be provided.

A supplementary analysis of partial response at both Week 24 and Week 52 will be undertaken using the alternative baseline definition (Section 6.2.2) of the lowest UPCR value pre-dosing.

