#### **Change from baseline endpoints**

Change from baseline in UPCR endpoints will be analyzed using a Mixed Effect Model Repeated Measures analysis with treatment arm, visit, treatment by visit interaction, biopsy class, MMF use at baseline, region and baseline UPCR included as a covariates in the model. Results will be expressed as differences between treatment arms (along with the associated 95% CI). The observed and change from baseline values will be summarized by treatment visit and treatment arms. The LS means and their corresponding 95% CI of the change from baseline values will also be presented for each visit and for the overall change. The model will be fitted using an unstructured (UN) covariance matrix. Should the UN covariance matrix not converge, then an autoregressive (AR(1)) covariance matrix will be used. The covariance matrix used will be indicated in the footnotes. The Kenward-Roger degree of freedom adjustment will be applied. LS mean plots of mean change from baseline versus visit will be presented for UPCR and eGFR.

The SAS code anticipated to be used for analysis of the change from baseline endpoints is as follows:

```
Proc Mixed data=dataset;  
Class Treatment biopsy_class MMF_use Region visit subject;  
Model response = Treatment biopsy_class MMF_use Region visit visit*treatment baseline/ DDFM=KR  
Repeated Visit/subject =subject Type= UN R Corr;  
LSmeans visit*treatment/PDIFF CL E;  
Run;
```

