## 9 CHANGES TO PLANNED PROTOCOL ANALYSIS

In the randomization, regional differences were not expected and blocking by region was done more for drug distribution reasons. While the analysis specified in the protocol stipulated that the regional blocking factor was not to be used in the analysis models, following feedback from regulatory agencies, the models will include terms for each of the factors used in the randomization process:

- Biopsy Class (Class V versus Others)
- MMF use at screening (Yes versus No)
- Region (North America, Latin America, Europe+South Africa and Asia Pacific)

During the regulatory agency review and feedback process it was decided to remove the ‘Duration of UPCR  $\geq 0.5$ ’ endpoint from the list of key-secondary endpoints and place it within the list of ‘Other Secondary Endpoints’. The proportion of subjects experiencing a confirmed  $>30\%$  decrease from baseline in eGFR at each timepoint was also removed from the list of key secondary endpoints. To this end, neither endpoint will form part of the hierarchical testing procedure.

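### Total weeks with UPCR ≤0.5 are compared by an unadjusted Wilcoxon test, although baseline UPCR and the randomisation factors are available and used in the SAP's main models; the test is valid but may lose some precision

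*SAP*

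**What the plan says.** SAP section 6.11.4.1 describes two analyses of the duration of UPCR ≤0.5 mg/mg.

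- **Main analysis.** Time from the first value at or below 0.5 to the second later value above it, among subjects who reached the threshold. It "will be analyzed in a similar manner to that described in Section 6.11.3.1", that is, by Kaplan-Meier and Cox. For the Cox model, section 6.11.3.1 states: "The model will include terms for treatment arm, baseline UPCR, biopsy class, MMF use at baseline and region".
- **Total weeks.** "An additional summary of this endpoint will be undertaken by summing the weeks" between each value at or below 0.5 and a later value above it. For this total, "comparison between both treatment arms will be carried out using a 2 sample Wilcoxon test". No strata or covariates are named.

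The same covariates appear in the other main efficacy models. Section 6.11.2.1 specifies a "logistic regression model with terms for treatment, baseline UPCR, biopsy class, MMF use at baseline and region". The change-from-baseline MMRM in section 6.11.4 has "biopsy class, MMF use at baseline, region and baseline UPCR included as a covariates in the model". Section 9 records that, after regulatory feedback, "the models will include terms for each of the factors used in the randomization process".

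Section 5 stratifies randomisation by biopsy class and screening MMF use, and uses four regions as a blocking factor. Sections 3.2.2 and 9 place the duration endpoint among the other secondary endpoints, outside the formal testing sequence.

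**The concern.** The Wilcoxon comparison departs from the SAP's main models without a stated reason. Baseline UPCR could well matter for this outcome. The target is an absolute value, whereas the entry criteria (Protocol section 5.2) set only a minimum UPCR of 1.5 or 2 mg/mg, depending on class, and no maximum. Subjects who start higher have further to fall, and should reach 0.5 later or not at all.

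Baseline UPCR is also not a randomisation factor, so chance imbalance is possible. Protocol section 1.2.4.2 reports a tendency to higher proteinuria in the Phase 2 arm that received the dose tested here. An unadjusted rank test would carry such an imbalance straight through, while the adjusted Cox analysis beside it would allow for it.

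What is at stake is the precision of one supporting comparison, and its consistency with the adjusted result reported beside it.

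**Working it through.** **1. The plan's own figure.** SAP section 4 gives 162 per arm for 80% power, with 20.0% against 34.4%, two-sided 0.05 and a continuity-corrected chi-square test. Recalculation gives 163 per arm, 79.9% power at 162, and an odds ratio of (0.344/0.656)/(0.20/0.80) = 2.10. The figure reproduces, but it concerns the primary endpoint. The documents state no power, effect size or standard deviation for the Wilcoxon comparison.

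**2. Why baseline UPCR may be prognostic.** The fall needed to reach 0.5 is 1 − 0.5/baseline. At entry UPCR 1.5 this is 1 − 0.5/1.5 = 67%. At an illustrative 5 it is 1 − 0.5/5 = 90%.

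**3. Effect of adjustment, normal approximation.** Let R² be the share of outcome-rank variance that the covariates explain. Adjustment multiplies the variance by 1 − R². If the unadjusted test has 80% power (an assumption),

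adjusted power = Φ((1.960 + 0.842)/√(1 − R²) − 1.960).

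For example, R² = 0.10 gives Φ(2.802/0.949 − 1.960) = Φ(0.993) = 84.0%. Leaving the covariates out is roughly like losing 324 × R² subjects, if all 324 are analysed.

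| R² (assumed) | Adjusted power | Gain (points) | 324 × R² |
|---|---|---|---|
| 0 | 80.0% | 0 | 0 |
| 0.05 | 82.0% | 2.0 | 16 |
| 0.10 | 84.0% | 4.0 | 32 |
| 0.15 | 86.0% | 6.0 | 49 |
| 0.20 | 87.9% | 7.9 | 65 |
| 0.30 | 91.8% | 11.8 | 97 |

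**4. Simulation with many zeros.** There were 324 subjects, permuted blocks within 2 × 2 × 4 = 16 strata, and 2,000 runs per setting. The outcome was floored at zero for 50% or 70% of placebo subjects. The effect size, stratum shares and prognostic strength are all assumptions. The Wilcoxon test was compared with rank analysis of covariance on baseline UPCR, biopsy class, MMF use and region.

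| Prognostic strength | 50% zeros: Wilcoxon → adjusted | 70% zeros: Wilcoxon → adjusted |
|---|---|---|
| None | 87.0 → 86.7% | 88.7 → 89.0% |
| Weak | 87.1 → 88.2% | 89.5 → 90.9% |
| Moderate | 86.3 → 90.3% | 89.4 → 91.0% |
| Stronger | 87.4 → 92.8% | 88.3 → 92.4% |
| Strongest (rank R² about 0.33 and 0.28) | 86.5 → 95.9% | 88.1 → 95.4% |

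The gain runs from about 0 to 9 points and is below 5 points in 7 of the 10 settings. The Monte Carlo standard error of each power is about √(0.87 × 0.13/2000) = 0.8 points.

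**5. Validity.** With no treatment effect, the Wilcoxon test rejected in 3.9 to 5.2% of runs and the adjusted test in 4.7 to 5.5%. Neither shows material inflation.

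**The case against.** The strongest reply is that this is an efficiency preference about a minor analysis. Much of that stands.

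- **The test is valid.** A reader might infer a faulty p-value from ignoring the stratification. The simulated error rates do not support that; any conservatism is slight.
- **Section 9 is not breached.** A reader might see a contradiction with its rule on randomisation factors. That rule speaks of models, and a two-sample Wilcoxon test is not one. Nor is this the only unadjusted comparison: section 6.11.4.2 uses chi-square or Fisher for eGFR decreases, and section 6.11.2.2 includes a deliberate treatment-only logistic model.
- **Little depends on it.** No alpha is allocated to it and no power was planned. Adjusted evidence on the same threshold comes from the duration Cox model and from the key secondary time to UPCR ≤0.5.
- **The analysis set is unclear.** A reader might take the weeks total as the comparison that keeps every randomised subject, unlike the responders-only Cox analysis. The text does not settle this. Section 6.11.4.1 limits the analysis of the endpoint to initial responders, then refers to a total for each subject, and section 6.11.4 names the ITT population. Nothing says that never-responders score zero. If only responders are meant, the sample size, the zeros and the simulated powers all change.

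A separate gap in the same paragraph should be closed too: time still at or below 0.5 at the last assessment has no stated counting rule.

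What survives is that relevant data already collected go unused, and that using them costs almost nothing. With no prognostic value, adjustment moved simulated power by no more than 0.3 points.

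**Conclusion.** The point holds as a low-cost improvement, at the lowest level of importance. The Wilcoxon test is unadjusted while the primary logistic, Cox and MMRM models carry baseline UPCR and all three randomisation factors. The cost is precision, and only if those covariates are prognostic. That is plausible for baseline UPCR, but the documents do not quantify it.

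From an assumed 80% base, the gain is about 0, 4 and 8 points at R² of 0, 0.10 and 0.20. These figures rest on the assumed base power and R², and the simulation also on an all-ITT analysis with never-responders at zero. The documents do not support an unconditional statement that the test gives away power, and no conclusion about the primary or key secondary endpoints is affected.

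**What to change.** In SAP section 6.11.4.1:

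- Make the arm comparison of total weeks a rank-based analysis of covariance, with terms for treatment, baseline UPCR, biopsy class, screening MMF use and region. If baseline UPCR is not to be used, a van Elteren test stratified by the randomisation factors is the alternative. With 16 cells and 324 subjects the average is 324/16 = about 20 per cell, so a rule for pooling sparse strata should be written in advance.
- Run it in all ITT subjects, and state that those who never reach 0.5 enter as zero weeks.
- Keep the unadjusted Wilcoxon test as a supportive result.
- Keep the descriptive summary in weeks beside it, because rank analysis of covariance reports a difference in ranks, not in weeks. That is the one small drawback.

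The cost is a sentence or two of SAP text and a few lines of code. No new data are needed.
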